16.7. Data Handling for Incidence Calculations

- Any infant with an RSV illness fulfilling the primary, secondary, or an exploratory efficacy endpoint will be counted once in the incidence analysis using the first episode even if this endpoint has been recorded multiple times and in several days.
- Any infant with an RSV illness fulfilling the primary, secondary, or an exploratory efficacy endpoint who dies before 90 days of age will be counted as having reached the endpoint and will be included in all subsequent analyses of 0-120, 0-150, and 0-180 days of age.
- Any infant who dies for of any illness other than an RSV LRTI will be included in the non-infected group for analysis.
- Two consecutive illness episodes that are within 7 days of each other will be combined as one continuous episode for the efficacy analysis.

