4. OBJECTIVE AND ENDPOINT

4.1. Study Objectives

4.1.1. Primary Objectives

- To determine the efficacy of maternal immunization with the RSV F vaccine against medically-significant RSV lower respiratory tract infection (LRTI) with EITHER hypoxemia (peripheral oxygen saturation [SpO_2] < 95% at sea level or < 92% at altitudes > 1800 meters) OR tachypnea (≥ 70 bpm for infants 0 to 59 days of age or ≥ 60 bpm for infants ≥ 60 days of age) through the first 90 days of life in infants of maternal RSV F vaccinees as compared to placebo recipients. In the event that efficacy is shown through the first 90 days of life, a hierarchical sequence of hypothesis tests will be carried out to examine efficacy through the first 120, 150, and 180 days of life.

The primary efficacy objective will be evaluated in term infants (≥ 37 weeks gestational age at delivery) born to maternal subjects who received a study injection ≥ 2 weeks (14 days) prior to delivery. Infants with multiple RSV episodes will be counted only once, using data from the first episode of medically-significant RSV LRTI. Success under the primary hypothesis will be achieved by demonstration of a lower bound of a two-sided 97.52% confidence interval for the Day 90 analysis (two-sided 95% confidence interval for later time points) for the estimate of vaccine efficacy which equals or exceeds target values agreed with regulatory authorities.

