10.2. Clinical Endpoint Adjudication Committee (CEAC)

A clinical endpoint adjudication committee (CEAC) comprising an odd number of three or more clinically-experienced voting pediatricians, a non-voting chair who will oversee meetings of the CEAC, and a non-voting coordinator for administrative support will be empaneled to review all primary, secondary, and exploratory efficacy endpoints relative to infant subjects. The operations of the CEAC will be carried out according to a charter which will be collaboratively drafted by the CEAC and the sponsor, and will be adopted prior to any review CEAC activities. The CEAC will review each potential efficacy endpoint event to determine whether the protocol-specified criteria have been fulfilled in a plausible temporal relationship. All deliberations of the CEAC will be carried out in blinded manner with regard to treatment

assignment and the determination of the CEAC with regard to each endpoint event will be final and binding on the sponsor.

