10.3. Analysis of Primary Efficacy Endpoints

The primary efficacy endpoint will be analyzed on the ITT-EFF-I and PP-EFF-I (infant) Populations. Conclusions concerning stopping for futility, the informational analysis, or declaration of attainment of the primary efficacy endpoint at the completion of the study, will only be based on the PP-EFF-I Population. In addition, supportive analyses based on the ITT-EFF-I Population will also be performed.

The Vaccine Efficacy (VE) is defined as $VE (\%) = (1 - RR) \times 100$, where RR = Relative Risk of incidence rates between the two treatment groups (RSV F Vaccine / Placebo). The final analysis will be carried out at one-sided Type I error rate of 0.0124 (i.e., the lower bound of two-sided 97.52% confidence interval). An estimate of vaccine efficacy will be reported using a two-sided 95% confidence interval. This conservative Type I error rate was determined as a part of the original group sequential design (GSD) approach and will be retained to guard against a potential Type I error inflation resulting from the decision to stop the study at ~4,600 maternal subjects given this decision occurred after the informational analysis. Since this change was not part of the original study design at the initiation of the study, the agreement on how to implement the change with respect to Type I error rate was finalized in consultation with the US-FDA.

For the original design using the GSD, a simulation of 5,000 trials was performed under a range of scenarios (including both varying placebo rates of medically-significant RSV LRTI and endpoint event ratios in infants of active vaccinees relative to placebo recipients). A summary of the simulation results is provided in the adaptive design for reference ([APPENDIX 1](#)).

The RR and its CI will be estimated using Poisson regression with Robust error variance [[Zou 2004](#)]. The generalized linear model with unstructured correlation matrix (Robust error variances) will be used. The explanatory variables in the model will include the treatment group. The dependent variable will be the incidence rate of the endpoint of interest. The Robust error variances will be estimated using repeated statement and the subject identifier. Poisson distribution will be used with a link function logarithm.

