- Updated the data cleaning plan for the final Day 180 unblinded analysis of efficacy and immunogenicity consistent with the submission provided to CBER on 16 November 2018 (SN 0187) specifying the data cleaning plan for the Day 180 unblinding. The initial plan for cleaning all efficacy, immunogenicity, and safety data for the Day 180 analysis was based on the original plan to submit the BLA with a Day 180 Clinical Study Report (CSR), with only partial Day 365 safety data available at the time of the original BLA submission (reference is made to BLA content proposal submitted in SN 0155; dated 27 April 2018). Per CBER's feedback on this proposal (reference is made to the CBER email dated 11 July 2018), a final CSR with Day 365 data for all subjects will be included in the BLA. Based on this feedback, the data cleaning plan was modified for the safety data at the time of the Day 180 efficacy unblinding. (Section 14.1)
- Added rules for determination of start and stop dates for whether concomitant medications were taken post-vaccination; for missing/incomplete suspect-illness start/stop dates; and for missing/incomplete admission and/or discharge dates for respiratory hospitalizations. (Section 16.6)
- Clarified how death will be handled in the efficacy analyses (Section 16.7)

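### SAP 16.7: the rule for deaths from other illnesses lacks an exception for infants who had already met the endpoint, and so conflicts with the two bullets before it

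*SAP*

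**What the plan says.** Three of the four bullets in SAP 16.7 bear on an infant who meets an endpoint and later dies.

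- First bullet: an infant whose RSV illness fulfils a primary, secondary or exploratory endpoint "will be counted once in the incidence analysis using the first episode even if this endpoint has been recorded multiple times". It sets no condition on survival.
- Second bullet: an infant who fulfils an endpoint and "who dies before 90 days of age will be counted as having reached the endpoint and will be included in all subsequent analyses", meaning the 0-120, 0-150 and 0-180 day windows. It does not restrict the cause of death, but it stops at Day 90.
- Third bullet: "Any infant who dies for of any illness other than an RSV LRTI will be included in the non-infected group for analysis". It has no age limit and no exception for an endpoint already met.

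Elsewhere, the primary endpoint is the percentage of infants with the event from delivery through 90, 120, 150 and 180 days (SAP 4.2.1). The primary objective (SAP 4.1.1) states: "Infants with multiple RSV episodes will be counted only once, using data from the first episode of medically-significant RSV LRTI". Under SAP 10.2 the "determination of the CEAC with regard to each endpoint event will be final and binding on the sponsor". The SAP change log for Version 6.0 (SAP 18.2) describes the edit to this section as follows: "Clarified how death will be handled in the efficacy analyses".

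**The concern.** Take an infant with an adjudicated medically-significant RSV LRTI on Day 40 who dies of an unrelated illness on Day 120. The first bullet counts this infant as a case. The third, taken literally, puts the same infant in the non-infected group, and because it names no window it would do so even in the 0-90 day primary analysis. The second bullet does not help, because the death falls after Day 90. If the death had come on Day 70, the second and third bullets would give opposite answers outright.

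At stake is who counts in the numerator of the primary, secondary and exploratory efficacy endpoints. An unrelated later death cannot undo an event that has already happened and been adjudicated. A programmer following the list could justify either answer, and the plan does not say which bullet prevails. The change log shows that this section is where the handling of deaths was meant to be settled.

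**Working it through.** **Reading the bullets together.** The possible infants, and what each bullet says of them:

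| Infant | First bullet | Second bullet | Third bullet |
|---|---|---|---|
| Endpoint met, dies of another illness before Day 90 | case | case | non-infected |
| Endpoint met, dies of another illness on Day 90 or later | case | silent | non-infected |
| Endpoint not met, dies of another illness | silent | silent | non-infected |
| Endpoint met, dies of RSV LRTI | case | case if before Day 90 | silent |

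The third row is the only one where the third bullet is both applicable and uncontested. In the first row it stands against two bullets. In the second it stands against the first bullet alone.

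**Inputs for scale.** From SAP 13: per-protocol infants n_v = 2,786 and n_p = 1,432; placebo rate 4%; vaccine efficacy (VE) 65%, so RR = 0.35 and the vaccine rate is 0.04 × 0.35 = 0.014; null boundary VE 30%, so RR = 0.70; stated power 87%. From SAP 10.3: one-sided Type I error 0.0124, which gives z = 2.2445.

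**The plan's own figure.** Normal approximation on the log relative risk:

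SE² = (1 − 0.014)/(2,786 × 0.014) + (1 − 0.04)/(1,432 × 0.04) = 0.986/39.004 + 0.96/57.28 = 0.0420, so SE = 0.205.

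Power = Φ(ln(0.70/0.35)/SE − 2.2445) = Φ(0.693/0.205 − 2.2445) = 87.2%, against 87% stated. It reproduces. None of these inputs depends on how deaths are classified, so planned power is not affected.

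**Effect of one reclassified infant.** Expected cases are 39.0 vaccine and 57.3 placebo, taken as 39 and 57. The infant stays in the denominator and leaves the numerator.

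VE = 1 − (x_v/2,786)/(x_p/1,432)

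Lower bound of the 97.52% interval = 1 − RR × exp(2.2445 × SE), with SE² = 1/x_v − 1/2,786 + 1/x_p − 1/1,432.

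| Vaccine cases | Placebo cases | VE | Lower bound |
|---|---|---|---|
| 39 | 57 | 64.8% | 44.3% |
| 38 | 57 | 65.7% | 45.5% |
| 39 | 56 | 64.2% | 43.2% |

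One infant moves VE by 0.6 to 0.9 points and the lower bound by 1.1 to 1.2 points. Losing a vaccine case raises VE and losing a placebo case lowers it. Across all combinations of 0 to 3 reclassified infants per arm, VE runs from 62.9% to 67.5% and the lower bound from 40.8% to 47.9%.

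**How many infants.** The documents give no rate of later non-RSV death among cases. Assuming 0.2% to 1%, the 39 + 57 = 96 expected cases yield 96 × 0.002 = 0.2 to 96 × 0.01 = 1.0 infants. That rate and the 0-to-3 range are assumptions used only to show scale.

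**The case against.** The best defence is that the section, read whole, already gives the right answer. The first bullet counts every infant who meets an endpoint, at any age and whatever follows. The second and third bullets can be read as a pair: deaths among infants with an endpoint, then deaths among the rest. On that reading the third bullet merely keeps infants who die of other causes in the denominator as non-cases. The label non-infected fits that reading, since every RSV LRTI endpoint needs RT-PCR detection of RSV. The objective, the endpoint definition and the binding adjudication all point the same way, and nothing suggests an intention to overturn confirmed cases.

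Most of this stands. A reader might infer from the third bullet that the SAP reclassifies confirmed cases; the documents do not support that, because the first two bullets say the contrary. A reader might also infer that cases who die between Day 90 and Day 180 are unprotected; that goes too far, because the first bullet covers them.

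What the defence does not remove is the literal conflict. The restriction that makes the paired reading work is not written in the third bullet. The Day 90 limit in the second is unexplained and invites the inference that later deaths are treated differently. No precedence is stated.

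**Conclusion.** The point holds as a drafting defect in a counting rule. The third bullet of SAP 16.7 omits the condition that the infant had not met the endpoint before death. As worded it is wrong for an infant who had, and it conflicts with the bullets before it and with SAP 4.1.1, 4.2.1 and 10.2.

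The practical effect is probably nil or a single infant, on the assumed death risk. At the design's expected counts, one infant would shift VE by less than one point and leave the lower bound well above 30%. A reader might suspect a bias towards the vaccine; none is shown, since the direction depends on the arm of the affected infant. A single infant would weigh more on a secondary endpoint with fewer cases, but the documents give no expected counts for those endpoints, so no figure can be put on it. This is a low-severity point, worth correcting because it leaves case status open to choice.

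**What to change.** Replace the second and third bullets of SAP 16.7 with:

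> An infant who met an endpoint before death remains a case for that endpoint in every window that contains the event, whatever the cause or date of death. An infant who dies of a cause other than RSV LRTI without having met the endpoint is a non-case.

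This restores agreement with the first bullet, the endpoint definition and the adjudication rule. It costs two sentences, needs no new data, and leaves the statistical method and sample size as they are. It should be settled before treatment codes are opened. If that has passed, the study report should state which reading was programmed and whether any infant was affected.

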16.8. Sensitivity Analyses of the Primary Endpoint

Sensitivity analyses for the primary efficacy endpoints will be performed to investigate the impact of missing specimens and visits for suspected medically-significant RSV LRTI. Whenever possible, supplemental data collected outside the study sites (i.e., hospitalization data within suspected RSV illness episodes) will be used for the sensitivity analysis instead of imputation. If there exists a hospital record for any components of the medically-significant RSV-LRTI endpoint definition, it will be used instead of imputations. These episodes will not be treated as missing.

In order to facilitate the assessment of other reasonable sensitivity assessments, a tipping point analysis will be performed by constructing a grid of all possible $(m_v + 1)$ by $(m_p + 1)$ imputed outcomes for missing values by assigning imputed number of “endpoints” from 0 to m_v in the vaccine group and 0 to m_p in the placebo group. For each possible imputed outcome, the overall vaccine efficacy and the corresponding confidence interval will be constructed using the same statistical method used for the primary efficacy endpoint. The imputed data points in the grid will be evaluated against the H_0 : Vaccine Efficacy $\leq 0\%$.

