6.2.3 Clinical Study Site Response to Reports of Initial Trigger Symptoms

In response to a report via active or passive surveillance of **Initial Trigger Symptoms**, the study site staff will:

- Arrange for an in-clinic or home visit as soon as possible, but not later than 7 days after symptom onset, for evaluation by the study physician/qualified clinical designee of the subject (infant or mother) displaying the symptom/s and/or findings listed in [Table 2](#).
- Arrange for an in-clinic or home visit by a study physician/qualified clinical designee for evaluation as soon as possible within 7 days of symptom(s) onset for maternal or infant subjects who received care for trigger symptoms at a non-study, affiliated medical facility. *Note that this visit would only be applicable to subjects who are receiving outpatient care or have been released from inpatient care.*

Procedures to Occur During the Visit:

- *Specific for Symptomatic Infants:* Measure the respiratory rate on room air (if possible) for all *symptomatic* infants. This measurement should be performed first, on a calm infant, and should be performed by observation only (i.e., without stethoscope auscultation) for a full, timed one minute period.
 - If the result is ≥ 60 bpm in an infant 0 to 59 days of age or ≥ 50 bpm in an infant ≥ 60 days of age, a second timed one minute count should be obtained.
 - If a second count is obtained, the lower of the two observations should be recorded.
- Measure the SpO₂ via pulse oximetry (using study-specific pulse oximeter) for all *symptomatic* infants, which is to be performed when the infant is calm and not crying, and before administration of oxygen supplementation. The lowest stable SpO₂ observed during a one minute measure should be recorded. *Note that the oxygen should not be removed to measure SpO₂ in infants already receiving oxygen supplementation at the time of assessment.* Please refer to the **Pulse Oximeter Manual** for more details.

For all Symptomatic Subjects (Maternal and Infant):

- Review and confirm the history of respiratory illness, including the approximate date of first symptom onset.
- Perform an examination of the *symptomatic* infant subject to ascertain, by observation or auscultation, the presence of the LRTI manifestations listed in [Table 3](#) below.
- Collect a respiratory specimen from the *symptomatic* subject for detection of respiratory viruses.

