4.2. Study Endpoints

4.2.1. Primary Efficacy Endpoint (In Infant Subjects)

- Percentages of infants with medically-significant RSV LRTI from delivery through 90, 120, 150, and 180 days of life, as defined by:
 - The presence of RSV infection confirmed by detection of the RSV genome by RT-PCR on respiratory secretions (obtained within the continuous illness episode which fulfills the other criteria listed below); AND
 - At least one manifestation of lower respiratory tract infection (LRTI) from among the following: cough, nasal flaring, lower chest wall indrawing, subcostal retractions, stridor, rales, rhonchi, wheezing, crackles/crepitations, or observed apnea; AND
 - Evidence of medical significance as defined by the presence of:
 - EITHER hypoxemia (peripheral oxygen saturation [SpO_2] < 95% at sea level or < 92% at altitudes > 1800 meters) OR
 - Tachypnea (\geq 70 breaths per minute [bpm] in infants 0 to 59 days of age and \geq 60 bpm in infants \geq 60 days of age).

Data elements supporting the three (3) criteria for a primary endpoint case will be present within the start and stop dates of a continuous illness episode and derived from clinical observations (LRTI signs and symptoms and respiratory rates) made by qualified clinical trial site staff, pulse oximetry performed by site personnel using a Masimo RAD-5 pulse oximeter supplied by the sponsor, and RSV detection based on study-specified RT-PCR performed by the validated GenMark eSensor assay in place at the central laboratory (Marshfield Clinic Research Institute, Marshfield, Wisconsin).

A Clinical Endpoint Adjudication Committee (CEAC) composed of expert pediatricians (see Section 10.2) will carry out a blinded review of all potential primary endpoint cases to determine if they fulfill the primary endpoint criteria in a temporally plausible relationship consistent with RSV disease as observed in clinical practice. Only CEAC-confirmed cases will be used for the primary endpoint.

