2. Calculating the event ratio, $r = \pi_v / \pi_p$ under each pair-wise sample from the posterior of π_v and π_p .

Futility stopping will be based on the posterior probability of futility that the event ratio is less than or equal to 0.60 is less than or equal to 0.05. Furthermore, an additional constraint governing the ability to stop the trial early for futility requires that a minimum of 10 events be observed in the vaccine arm. All futility analyses will include all infant subjects who are 90 days old at the time of the data cutoff date.

In addition as a sensitivity analysis, time to the first medically-significant RSV LRTI event will be analyzed by treatment group using Kaplan-Meier methods taking potential differences in the length of subject follow-up into account. Sub-analyses will be performed to evaluate vaccine effects on all infections in which RSV is confirmed by RT-PCR, and also infections in which only RSV is found (i.e., no co-infections). The incidence rate of medically-significant RSV LRTI may be generated by age stratum or co-morbidities present, if sufficient event numbers are available.

Sensitivity analyses for the primary efficacy endpoint will be performed to investigate the impact of missing specimens for suspected-RSV illnesses, including RSV-negative specimens collected outside the specified collection window, and clinical assessments, including clinical signs/symptoms, respiratory rates, and pulse oximetry measurements, obtained by non-study healthcare providers (e.g., hospitalization records). Further details are presented in Section 16.8.

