16.6. Missing, Unused, and Spurious Data

In general, there will be no substitutions made to accommodate missing data points. All data recorded on the eCRF will be included in data listings that will accompany the CSR.

For maternal subjects, if delivery date is missing, it will be imputed as the estimated delivery date (EDD) to establish the projected end time for their efficacy analysis.

When tabulating AE data, partial dates of AE onset will be handled as follows:

- If the day of the month is missing, the onset date will be assumed to be the date of either the first, in order to conservatively report the event as vaccine-emergent, unless the month reported clearly indicates the event would be outside the window for vaccine-emergent events, in which case no date will be imputed.
- If the onset day and month are both missing, the event onset will be coded to the day of vaccination (the birth date for infant subjects) in order to conservatively report the event as vaccine-emergent, unless it is clear by reference to the year that the event is outside the window for vaccine-emergent events.
- A completely missing onset date will be coded as the day of vaccination.

A conservative approach will be taken to assess the relationship of an AE to vaccine: if the relationship of an event is missing, it will be considered treatment-related. Missing severity for an AE will not be imputed.

When determining whether the concomitant medication was taken post-vaccination (i.e., start date is on or after the vaccination date), missing or incomplete start date will be handled as follows:

- If the start date is completely missing and the reason for use is not marked as preexisting, it will be treated as post-vaccination.
- If only the year is provided and the year is on or after the year of the vaccination and the reason for use is not marked as preexisting it will be treated as post-vaccination.
- If only the year and month are provided and the year and month are on or after the year and month of the vaccination and the reason for use is not marked as preexisting it will be treated as post-vaccination.

When tabulating concomitant medications data associated with the RSV surveillance illnesses, partial or missing dates of start and stop will be handled as follows:

- If a start date is completely missing, it will be assigned as Day 14 (start of the RSV surveillance for each subject) for maternal subjects (the birth date for infant subjects).

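### The tipping-point rule in SAP 16.8 drops a whole episode from the missing set on the strength of one hospital-recorded component, so an infant with no RSV result from any source is fixed as a non-case

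*SAP*

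**What the plan says.** SAP 10.3 promises sensitivity analyses of the "impact of missing specimens for suspected-RSV illnesses", and SAP 16.8 gives the details. Its aim is to "investigate the impact of missing specimens and visits for suspected medically-significant RSV LRTI". The tool is a tipping-point grid of "imputed outcomes for missing values by assigning imputed number of" endpoints, from 0 to m_v in the vaccine arm and from 0 to m_p in the placebo arm. Each cell is analysed by the primary method and judged against VE ≤ 0%.

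Before the grid is built, hospital data are brought in: "If there exists a hospital record for any components of the medically-significant RSV-LRTI endpoint definition, it will be used instead of imputations". The next sentence reads: "These episodes will not be treated as missing".

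Three other provisions matter:

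- SAP 4.2.1 joins three criteria by AND. The first is "The presence of RSV infection confirmed by detection of the RSV genome by RT-PCR on respiratory secretions"; the others are an LRTI manifestation, and hypoxemia or tachypnea.
- SAP 16.6 gives the default for missing data: "In general, there will be no substitutions made to accommodate missing data points".
- Protocol 6.2.3, on subjects treated at a non-study facility, notes that "this visit would only be applicable to subjects who are receiving outpatient care or have been released from inpatient care".

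**The concern.** The trigger works at component level, but the consequence works at episode level. One charted component of any kind is enough to take the whole episode out of the missing set, even when the component that is absent is the RT-PCR result.

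A charted SpO2 says nothing about whether RSV was present. An infant admitted with respiratory illness, with no study swab and no local RSV test, has unknown case status. Under the rule that infant is not counted in m_v or m_p and is never imputed. The grid then varies only the episodes that have no hospital record, while some hospitalised infants with an unknown outcome are held fixed as non-cases. A statement that no plausible allocation of the missing outcomes overturns the result would not cover them.

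**Working it through.** **Step 1: follow one episode through the rules.** Take an infant whose hospital chart records SpO2 below the threshold, with no RSV result from site or hospital.

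1. A hospital record exists for one component, so it is used instead of imputation (16.8).
2. The episode is therefore not missing (16.8) and lies outside m_v and m_p.
3. RT-PCR positivity is mandatory (4.2.1) and is absent, so the infant cannot be a case.
4. Nothing is generally substituted (16.6), so the status stays non-case in all (m_v + 1) × (m_p + 1) cells.

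Steps 1 and 2 are the SAP's wording. Steps 3 and 4 are inference from it. Neither document has a separate rule for partial hospital records.

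**Step 2: check the inputs against the plan's own figure.** SAP 13 gives 87% power for 2,786 vaccine and 1,432 placebo infants, placebo rate 4%, VE 65%, null VE < 30%, one-sided 0.0124. On the log risk-ratio scale:

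- SE = √[(1 − 0.014)/(2,786 × 0.014) + (1 − 0.04)/(1,432 × 0.04)] = 0.2050
- (ln 0.70 − ln 0.35)/0.2050 = 3.381; less z = 2.2445 gives 1.136
- Φ(1.136) = 87.2%

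A constrained score form gives 87.5% and matches all 25 cells of the power table within half a point. The inputs are confirmed.

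**Step 3: how many extra vaccine-arm cases tip the grid?** With treatment as the only covariate, robust Poisson gives, up to a small-sample factor, the Wald interval for log RR:

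- RR = (x_v/2,786)/(x_p/1,432)
- SE² = 1/x_v − 1/2,786 + 1/x_p − 1/1,432
- lower bound of VE = 1 − RR × exp(2.2445 × SE)

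Observed counts are assumed to be the rounded expected counts. Cases are added to the vaccine arm only, with none added to placebo, until the 97.52% lower bound is 0 or below. The denominators do not change, because these infants are already in the population.

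Example (placebo 3%, VE 65%): 29 against 43 cases gives RR 0.3467, SE 0.2381 and lower bound 40.8%. With 53 vaccine cases the bound is 0.2%; with 54 it is −1.5%. So 54 − 29 = 25 extra cases are needed.

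| Placebo rate | VE | Cases, placebo / vaccine | Lower bound at start | Extra vaccine cases to tip |
|---|---|---|---|---|
| 2% | 50% | 29 / 28 | 10.5% | 4 |
| 2% | 65% | 29 / 20 | 32.2% | 12 |
| 3% | 50% | 43 / 42 | 18.7% | 12 |
| 3% | 60% | 43 / 33 | 34.0% | 21 |
| 3% | 65% | 43 / 29 | 40.8% | 25 |
| 4% | 50% | 57 / 56 | 23.5% | 20 |
| 4% | 60% | 57 / 45 | 36.9% | 31 |
| 4% | 65% | 57 / 39 | 44.3% | 37 |

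**Step 4: illustrate the omission.** Take placebo 3%, VE 50% and, as an assumption, m_v = 5. The worst cell has 47 vaccine cases and a lower bound of 10.3%, so no cell tips. If omitted vaccine-arm episodes are put into the grid, the worst-cell bound becomes 1.8% (5 episodes), −6.6% (10) or −23.4% (20). The documents give neither m_v nor the number omitted.

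**The case against.** **The rule may be meant by component.** Using a hospital record instead of imputation can be read as replacing only the imputation of that component. That may be the intent, but the sentence that follows refers to episodes and does not support it.

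**Hospitalised infants are not out of reach.** A reader might infer from the note in protocol 6.2.3 that they are never sampled. The documents do not say so. Protocol 6.2.4 encourages an in-hospital follow-up visit where locally permitted, with the same procedures, including the swab. The note itself qualifies one bullet, which still arranges a visit within 7 days of onset after release from inpatient care. The rationale for protocol version 9.0 (Appendix 5) describes infants seen by the site first and admitted 2 to 3 days later. Since a site visit includes a swab, what they typically lack is a later SpO2 or respiratory rate, which a hospital record properly supplies. This narrows the group. It does not empty it, because the in-hospital visit is encouraged, not required, and the version 10.0 change history mentions infants taken directly to hospital.

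**A handful of cases would overturn the result.** A reader might infer this from the 30% criterion used for the US-FDA. At the 97.52% bound, 3 (placebo 3%, VE 60%), 7 (3%, 65%), 6 (4%, 60%) or 12 (4%, 65%) extra vaccine cases bring the lower bound below 30%. But SAP 16.8 judges the grid against VE ≤ 0%, where the same scenarios need 21, 25, 31 and 37. The smaller figures do not describe this analysis.

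**It is supportive only.** The primary estimate, alpha and decision rule are untouched. Hospital records, including local RT-PCR, also feed an exploratory version of the primary endpoint (SAP 4.2.3 and 4.2.3.1). Both points stand, but neither resolves an infant with no RSV test at all.

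**Conclusion.** The concern holds in a limited form. Followed literally, the rule classifies an unknown RSV status as known, in an analysis whose declared subject is missing specimens. It affects only infants with at least one hospital-recorded component, no RSV result from any source, and no record that rules out a case. Where SpO2 and respiratory rate stayed outside the criteria throughout, non-case status is legitimate. Where a local positive result completes the definition, the infant counts as a case in the sensitivity analysis.

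It would go too far to say that the analysis will look more robust than it is. The number of such infants is not in the documents and could be zero, and their split by arm is unknown. Counting them would widen the grid in both directions; where the truth would fall cannot be said. What can be said is that the grid could look more robust than it is, mainly when the observed effect is modest, events are few, or many such episodes exist. For an observed VE of 60 to 65% at placebo rates of 3 to 4%, tipping would need 21 to 37 such infants, all in the vaccine arm and all RSV cases.

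These counts rest on assumed event counts, the planned per-protocol sizes and the 97.52% bound. SAP 16.8 does not name the interval level for the grid. At 95% the counts rise slightly: 4 becomes 7 (2%, VE 50%), 12 becomes 15 (3%, 50%), 25 becomes 28 (3%, 65%) and 37 becomes 41 (4%, 65%).

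**What to change.** Replace the two sentences in SAP 16.8 with:

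> Hospital data will replace a missing component only for that component. An episode is treated as non-missing only if combined site and hospital data establish all three components or one known component rules out a case. All other episodes, including hospitalised episodes without an RT-PCR result, count in m_v or m_p, and their number will be reported by arm.

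The cost is a short text change and one programming flag, set before unblinding. The robustness statement may come out slightly less favourable. If few such episodes exist, the results barely change and the count by arm shows why.
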